^aAttribution: 1 = unrelated, 2 = unlikely, 3 = possible, 4 = probable, 5 = definite.

^bRECIST criteria: NE, not evaluable.

[figure not shown]
^cDid not complete study therapy.

Pharmacokinetics analyses:

In the phase 1 trial, PK analyses demonstrated achievable and sustainable levels of plasma IUDR $\geq 1 \mu\text{M/L}$ (levels previously shown to mediate radiosensitization) at dose levels $\geq 600\text{mg/day}$ (Figure 4).

Figure 4: PK analyses – Phase 1 trial and pharmacology trial of oral IPdR as a prodrug for IUDR-mediated radiosensitization in patients receiving palliative RT for metastatic GI cancers (NCI #9882) (Kinsella *et al.*, 2019).

(A) Mean plasma concentrations of IUDR by IPdR dose level. (B) Plasma concentrations of IUDR in individual patients on Days 1, 15, and 22 at 1200 mg dose level (MTD, recommended phase 2 dose [RP2D])

Although not the primary objective of the study, all patients had measurable disease at study entry. Evaluation of target lesions within the radiation field 4 weeks following completion of therapy (at Week 8), using Response Evaluation Criteria in Solid Tumors (RECIST) criteria, revealed two Complete Response (CR), three Partial Response (PR), nine Stable Disease (SD), and no progressive disease (PD) in these patients.

In conclusion, this first-in-human tolerance study of IPdR confirmed that IPdR is predictably and readily absorbed following PO administration, is metabolized to IUDR principally by hepatic aldehyde oxidase, and demonstrates PK that compare favorably to those of IUDR. The administration of IPdR PO QD \times 28 days with RT is feasible and tolerable at doses that produce plasma IUDR levels $\geq 1\mu\text{M/L}$, achieving plasma IUDR levels that have previously been associated with clinically significant radiosensitization. This phase 1 study supports further testing of IPdR as a potential radiosensitizing agent. In this subsequent trial, we propose evaluating the addition of PO IPdR to preoperative capecitabine + RT for patients with rectal cancer.

2.3 Other Agents

2.3.1 Capecitabine

Capecitabine is a fluoropyrimidine carbamate with antineoplastic activity. It is an orally administered systemic prodrug of 5'-deoxy-5-fluorouridine (5'-DFUR) which is converted to 5-fluorouracil (5-FU) *in vivo*. Both normal and tumor cells metabolize 5-FU to 5-fluoro-2'-deoxyuridine monophosphate (FdUMP) and 5-fluorouridine triphosphate (FUTP). These metabolites cause cell injury by two different mechanisms. First, FdUMP and the folate cofactor, N^{5,10}-methylenetetrahydrofolate, bind to thymidylate synthase (TS) to form a covalently bound ternary complex. This binding inhibits the formation of thymidylate from 2'-deoxyuridylate. Thymidylate is the necessary precursor of thymidine triphosphate (TTP), which is essential for the synthesis of DNA, so a deficiency of this compound can inhibit cell division. Second, nuclear transcriptional enzymes can mistakenly incorporate FUTP in place of uridine triphosphate (UTP) during the synthesis of RNA. This metabolic error can interfere with RNA processing and protein synthesis.

2.3.1.1 Capecitabine + RT: ChemoRT phase of LARC therapy:

Fluoropyrimidine therapy concurrent with RT for rectal cancer currently represents the standard of care for this disease (Sauer *et al.*, 2004). The Gastrointestinal Tumor Study Group showed that adjuvant combined modality therapy with RT and 5-fluorouracil (5-FU)-based chemotherapy improved outcomes in patients with rectal cancer both in terms of local control OS compared to postoperative RT alone (Krook *et al.*, 1991). The incorporation of protracted infusional 5-FU with RT further improved clinical outcomes (O'Connell *et al.*, 1994). NSABP R-04 demonstrated similar clinical outcomes between capecitabine and continuous infusion 5-FU when added to RT for rectal cancer (O'Connell *et al.*, 2014). Pathologic complete responses were similar between the two arms (22.2 vs. 18.8%; *p*=0.12) while toxicity clinically favored capecitabine.

2.4 Rationale

[figure not shown]
2.4.1 Mechanism of fluoropyrimidine (FP)-based radiosensitization (RS) and interactions of IPdR on FP-based binding (inhibition) of thymidylate synthetase (TS) to enhance FP-RS:

While the precise mechanisms of FP-mediated RS of rectal tumors are not clearly understood, we and others have shown experimentally that RS is principally mediated by FP effects on the production and balance of intracellular DNA nucleotide pool via binding of the principal FP metabolite, FdUMP, to TS causing TS inhibition and depletion of dTTP pools (Bruso *et al.*, 1990; Miller and Kinsella, 1992). The level of TS expression in colorectal cancer (CRC) cell lines and in patient tumor specimens is of prognostic significance where high TS expression correlates with reduced RS (Miller and Kinsella, 1992). In experimental studies, the addition of IPdR further inhibits TS with a greater than additive effect as a result of the generation of the intracellular IPdR monophosphate metabolite, IdUMP that further inhibits (by binding) TS leading to increased FP-mediated RS (Lawrence *et al.*, 1992; Miller *et al.*, 1995).

2.4.2 FP + IPdR/IUDR:

The phase 1 and clinical pharmacology study combining a fluoropyrimidine (fluorodeoxyuridine, FUDR) and a halogenated pyrimidine (HP) analog (IUDR) provides data that may be applied to the combination of capecitabine + IPdR proposed in this study (Speth *et al.*, 1988). FUDR and IUDR were administered concomitantly, as 14-day continuous intravenous (IV) infusions with standard fractionated RT. The majority of patients in this study had glioblastoma multiforme (GBM), and the trial tested the hypothesis that FP would modulate the extent of cellular %IUDR-DNA incorporation (Speth *et al.*, 1988). In retrospect, GBM was a poor choice for testing this hypothesis in light of the limited FP cytotoxicity in this tumor. However, using %IUDR-DNA incorporation in circulating granulocytes as a biochemical endpoint and both fixed and escalating doses of either FUDR or IUDR, no modulation of %IUDR-DNA incorporation was found in the granulocytes. Indeed, the different MTDs of IUDR and FUDR plotted in an isobologram suggested only additive effects (Figure 5). Additionally, no changes in the expected plasma levels of either drug were found. This clinical study provides data regarding the concomitant use of a FP and IUDR as radiosensitizers.

Figure 5: Isobogram of the relationship between the MTDs of FdUrd and IdUrd administered as single agents or co-administered in different dosage combinations (Speth *et al.*, 1988)

In contrast, RT + FP (using either continuous infusion 5-FU for up to 96 hours or twice daily PO capecitabine) is an internationally established treatment for LARC with acceptable acute and late normal tissue toxicities (Table 1). Three *in vivo* preclinical studies in two representative CRC (HT29 and HCT-116) xenograft models supporting the superiority of PO IPdR given daily or up to three times a day *vs.* continuous infusion IUdR (at the MTD) as a radiosensitizer demonstrating an improved therapeutic index have been published (Kinsella *et al.*, 1994; Kinsella *et al.*, 1998; Seo *et al.*, 2004)

2.4.3 Twice-a-Day Dosing of IPdR:

Based on laboratory studies by Seo *et al.*, 2005 and discussions with [name] (Developmental Therapeutics Program [DTP], NCI), this protocol will utilize a twice a day (BID) dosing schema of IPdR with capecitabine and RT. Seo *et al.*, evaluated and compared four different IPdR treatment schedules: once a day, three-times a day, every-other-day, and every third day. Plasma PK, IUdR-DNA incorporation in tumor and normal proliferating tissues, tumor growth delay following irradiation, and body weight loss were used as end points. The three-times-daily schedule with the same total daily doses as the daily schedule improved the efficiency of IPdR conversion to IUdR. This study will initially utilize a twice daily schedule to correspond to capecitabine administration.

Based on IPdR's interactions with FPs and RT in preclinical studies, IPdR is expected to improve the efficacy of the chemoRT phase of treatment for patients with LARC. This phase 1 study will determine the MTD of the concomitant administration of IPdR with capecitabine + RT. The favorable toxicity profile of IPdR given with concurrent RT in NCI #9882 provides support for the expected tolerability of this chemoRT combination (IPdR + capecitabine + RT). NRG Oncology TNT trial (NRG-GI002; NCT02921256) is a multi-arm randomized phase 2 modular clinical trial platform utilizing TNT with parallel experimental arms. Because patients on this trial will receive identical treatment to those on NRG-GI002 (minus IPdR), results of this

trial will facilitate expeditious incorporation of IPdR into NRG-GI002 as an experimental arm.

2.5 Correlative Studies Background

2.5.1 IPdR PK

On Day 8, plasma PK analyses will be performed. A 10 cc blood sample will be obtained just prior to the PO IPdR dose and then at 30, 60, 120, and 240 minutes following the PO dose of IPdR. On Days 21 and 35, 10 cc of blood will be drawn 1-2 hours following the PO dose of IPdR for plasma IPdR and IUDR levels.

Methodologies for the PK analyses are those detailed and reported previously (Kummar *et al.*, 2013) and the same as used in the prior phase 1 trial (Kinsella *et al.*, 2019). Employing a similar schedule for PK sampling in this trial as that used in the prior phase 1 study will allow comparison of the results, and the potential impact of concomitant capecitabine dosing.

2.5.2 Capecitabine PK

Levels of capecitabine and its metabolites will be performed on Days 8, 21, and 35 in conjunction with the IPdR PK studies, using a portion of the 10-mL blood samples described above (Section 2.5.1).

Methodologies for the capecitabine PK analyses are those detailed and reported previously (Reigner *et al.*, 2001).

2.5.3 %IUDR-DNA cellular incorporation into tumor biopsy specimen

As the %IUDR-DNA cellular incorporation in human tumor xenografts in athymic mice was linearly related to the IPdR dose when given PO QD \times 6-14 days (Kinsella *et al.*, 1994; Kinsella *et al.*, 2000b; Seo *et al.*, 2004), we will evaluate for correlation between %IUDR-DNA cellular incorporation in tumor cells obtained from the surgical resection specimen and the dose of IPdR received as a biomarker of tumor radiosensitization. Evaluation for correlation of tumor response using pCR rate and NAR score and the %IUDR-DNA cellular incorporation in tumor cells obtained from the surgical resection specimen will also be performed.

2.5.4 %IUDR-DNA cellular incorporation in peripheral (circulating) granulocytes:

%IUDR-DNA cellular incorporation in peripheral (circulating) granulocytes will be performed as a biomarker of bone marrow acute normal tissue toxicity. These analyses will be performed at three time points on study, Days 8, 21, and 35. %IUDR-DNA cellular incorporation in peripheral (circulating) granulocytes will be correlated with peripheral blood counts, other systemic toxicities (CTCAE v5.0) and plasma PK obtained at the same time points. This assay was originally developed in [name]' laboratory at NCI (Belanger *et al.*, 1986; Belanger *et al.*, 1987).

Based on our pre-clinical data regarding %IUDR-DNA cellular incorporation in bone marrow

cells harvested directly from the femurs of athymic mice and ferrets following a 14 day exposure to PO QD IPdR (Kinsella *et al.*, 1994; Kinsella *et al.*, 2000; Seo *et al.*, 2004; Seo *et al.*, 2005) we would not expect a significant correlation between the %IUDR-DNA cellular incorporation in circulating granulocytes and PK measurements, peripheral blood counts, or systemic toxicities.

We have used circulating granulocytes as surrogate cells for bone marrow toxicity using the %IUDR-DNA cellular incorporation in several clinical trials of continuous intravenous (ci) IUDR (Belanger *et al.*, 1986; McGinn *et al.*, 1996; Schulz *et al.*, 2004; Seo *et al.*, 2004). For example, using a 28-day schedule of ci IUDR, we found an increase in the %IUDR-DNA incorporation in circulating granulocytes that: peaked by Day 21 of the 28-day ci treatment; reached nearly 5% at the highest dose level (781 mg/m²/day); correlated with steady-state plasma IUDR of 1.5 ± 0.3 µM; and was associated with Grade 4 neutropenia in 2 of 6 patients and Grade 3 thrombocytopenia in 1 of 6 patients (Schulz *et al.*, 2004). In contrast, PO QD dosing of IPdR at 1 gm/kg/day × 28 days in rats showed no significant myelosuppression and %IUDR-DNA incorporation <2% with steady-state plasma IUDR levels of 2-3 ± 0.5 µM.(Schulz *et al.*, 2004)

3. PATIENT SELECTION

This study involves the chemoradiotherapy phase of treatment for LARC. The intent is for patients to receive treatment as per NRG-GI002 with the addition of IPdR during the chemoradiotherapy phase. As such, patients must have been diagnosed with LARC and received 8 cycles of mFOLFOX6 (Appendix E) prior to study entry, with the intent to undergo surgical resection following chemoradiotherapy.

3.1 Eligibility Criteria

- 3.1.1 At diagnosis, patients must have had histologically proven adenocarcinoma of the rectum with no evidence of distant metastases.
- 3.1.2 At diagnosis, the major portion of the tumor must have been intact, and the following must be documented:
 - distance of the lowest tumor margin from the anal verge; *and*
 - intent for sphincter sparing or non-sphincter sparing surgical resection according to the primary surgeon; *and*
 - the majority of the untreated tumor must be <12 cm from the anal verge or below the peritoneal reflection as determined by the treating surgeon.
- 3.1.3 At diagnosis, the tumor must have been locally advanced Stage II (T3-4 N0) or Stage III (N+) rectal cancer with at least one of the following:
 - *Distal location (as defined by measurement on MRI, ERUS/pelvic CT [with IV contrast] scan or palpable on digital rectal exam [DRE]):* cT3-4 ≤5 cm from the anal verge, any N
 - *Bulky:* any cT4 or evidence that the tumor is adjacent to (defined as within 3 mm of) the mesorectal fascia on MRI or ERUS/pelvic CT (with IV contrast) scan
 - *High risk for metastatic disease* with 4 or more regional lymph nodes (cN2). **Clinical**

Nodal or "cN" status for eligibility includes the total number of nodes (N2 = 4 or more) in the mesorectal and superior rectal stations measuring ≥ 1.0 cm in any axis on cross sectional or endoscopic imaging. Nodes must measure 1.0 cm or greater to be considered positive for this eligibility requirement.

- *Not a candidate for sphincter-sparing surgical resection prior to neoadjuvant therapy* (as planned by the primary surgeon)

3.1.4 Patients must have received 8 cycles of neoadjuvant mFOLFOX and must have completed this therapy at least 3 weeks (and no more than 6 weeks) prior to enrollment on this study (see Appendix E).

3.1.5 Patients must intend to undergo surgical resection of the rectal primary tumor following chemoradiotherapy.

3.1.6 Age ≥ 18 years.

Because no dosing or adverse event (AE) data are currently available on the use of IPdR in combination with Capecitabine and RT in patients < 18 years of age, children are excluded from this study, but will be eligible for future pediatric trials.

3.1.7 ECOG performance status ≤ 2 (Karnofsky $\geq 60\%$, see Appendix A).

3.1.8 Patients must have adequate organ and marrow function as defined below:

- leukocytes	$\geq 3,000/\text{mcL}$
- absolute neutrophil count	$\geq 1,200/\text{mcL}$
- platelets	$\geq 100,000/\text{mcL}$
- hemoglobin	$> 10 \text{ g/dL}$
- total bilirubin	$\leq 1.5 \times$ institutional upper limit of normal (ULN)
- AST(SGOT)	$\leq 2.5 \times$ institutional ULN
- ALT(SGPT)	$\leq 2.5 \times$ institutional ULN
- creatinine	$\leq 1.5 \times$ institutional ULN
OR	
- glomerular filtration rate (GFR)	$\geq 60 \text{ mL/min}/1.73 \text{ m}^2$ (see Appendix B)
- alkaline phosphatase	$\leq 3 \times$ institutional ULN
- sodium, potassium, chloride, bicarbonate and magnesium	Within institutional normal limits

3.1.9 Patients with acquired immunodeficiency syndrome (AIDS-related illnesses) or known human immunodeficiency virus (HIV) disease **must**:

- Have a CD4 count $\geq 200 \text{ cells}/\mu\text{L}$ within 30 days before enrollment,
- Be off all antiretroviral therapy (prophylaxis/treatment) more than 60 days before

enrollment, and

- Have no evidence of opportunistic infections.

3.1.10 Patients with a history of hepatitis C virus (HCV) infection must have been treated and cured and be receiving no therapy.

3.1.11 Patients with known history or current symptoms of cardiac disease, or history of treatment with cardiotoxic agents, should have a clinical risk assessment of cardiac function using the New York Heart Association Functional Classification. To be eligible for this trial, patients should be class 2B or better.

3.1.12 Patients must have the ability to swallow and retain oral medication.

3.1.13 The effects of IPdR on the developing human fetus are unknown. For this reason and because radiosensitizing agents as well as other therapeutic agents used in this trial are known to be teratogenic, women of child-bearing potential (WOCBP)* and men must agree to use adequate contraception (hormonal or barrier method of birth control; abstinence) prior to study entry and for the duration of study participation. WOCBP must have a negative urine or serum pregnancy test within 72 hours prior to enrollment. If urine pregnancy results are positive or cannot be confirmed as negative, a serum pregnancy test will be required. Should a woman become pregnant or suspect she is pregnant while she or her partner is participating in this study, she should inform her treating physician immediately. Men treated or enrolled on this protocol must also agree to use adequate contraception prior to the study, for the duration of study participation, and 4 months after completion of IPdR administration.

*Women of childbearing potential (WOCBP) is defined as any female who has experienced menarche and who has not undergone surgical sterilization (hysterectomy or bilateral oophorectomy) or who is not postmenopausal. Menopause is defined clinically as 12 months of amenorrhea in a woman over 45 in the absence of other biological or physiological causes.

3.1.14 Ability to understand and the willingness to sign a written informed consent document. Participants with impaired decision-making capacity (IDMC) who have a legally-authorized representative (LAR) and/or family member available will also be eligible.

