3.2 Exclusion Criteria

3.2.1 Patients who have not recovered from adverse events due to prior mFOLFOX6 chemotherapy (*i.e.*, have residual toxicities > Grade 1) with the exception of alopecia.

3.2.2 Patients who are receiving any other investigational agents.

3.2.3 Patients with impaired GI function or GI disease that may significantly alter the absorption of oral IPdR and capecitabine (*e.g.* ulcerative disease, uncontrolled nausea, vomiting, diarrhea, malabsorption syndrome, or small bowel resection). Patients with

active inflammatory bowel disease (*i.e.*, patients requiring current medical interventions or who are symptomatic) or have a history of abdominal surgery or other medical condition that may, in the opinion of the treating physician, interfere with GI motility or absorption. Patients with colostomies are allowed unless colostomy is for one of the precluded reasons above.

- 3.2.4 Treatment with warfarin is not allowed. However, therapy with heparin, low molecular weight heparin (LMWH), and DOACs (Direct oral anticoagulating agent) such as dabigatran (Pradaxa), rivaroxaban, and apixaban [Eliquis] is allowed.
- 3.2.5 Patients with an active concurrent invasive malignancy.
- 3.2.6 History of prior invasive rectal malignancy, regardless of disease-free interval.
- 3.2.7 Patients who have received pelvic RT for rectal cancer, or prior pelvic RT for any other malignancy that would prevent the patient from receiving the required RT for this study.
- 3.2.8 History of allergic reactions attributed to compounds of similar chemical or biologic composition to IPdR or capecitabine.
- 3.2.9 Patients with uncontrolled intercurrent illness.
- 3.2.10 Patients with psychiatric illness/social situations that would limit compliance with study requirements.
- 3.2.11 Pregnant women are excluded from this study because IPdR may have the potential for teratogenic or abortifacient effects. Because there is an unknown but potential risk for adverse events in nursing infants secondary to treatment of the mother with IPdR, breastfeeding should be discontinued if the mother is treated with IPdR. These potential risks may also apply to other agents used in this study.

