11. STUDY CALENDAR

Baseline evaluations are to be conducted within 1 week prior to start of protocol therapy. Scans and X-rays must be done \leq 4 weeks prior to the start of therapy. In the event that the patient's condition is deteriorating, laboratory evaluations should be repeated within 48 hours prior to

initiation of the next cycle of therapy.

NCI Protocol #: 10410
 Version Date: June 2, 2022

	Pre-Study	Wk 1	Wk 2	Wk 3	Wk 4	Wk 5	Wk 6	Wk 10 (4 wks following chemoRT) End of study for toxicity assessment	Wk 14-18 (8-12 wks following chemoRT) End of study for response assessment
IPdR		A	A	A	A	A	A		
Capecitabine		B	B	B	B	B	B		
Radiation therapy		C	C	C	C	C	C		
Surgical resection									X
mFOLFOX6 × 8 cycles	X								
Informed consent	X								
Demographics	X								
Medical history	X								
Concurrent meds	X	X	X	X	X	X	X	X	X
Physical exam	X	X	X	X	X	X	X	X	X
Vital signs	X	X	X	X	X	X	X	X	X
Height	X								
Weight	X	X	X	X	X	X	X	X	X
Performance status ^a	X	X				X		X	X
CBC w/diff, plts	X	X	X	X	X	X	X	X	X
Carcinoembryonic Antigen (CEA)	X							X	X
Comprehensive Chemistry Panel ^b	X	X	X	X	X	X	X	X	X
EKG (as indicated)	X								
Blood draws for PK and IUDR incorporation in granulocyte assays (mandatory)			X ^{c,d}	X ^{c,d}		X ^{c,d}			
Adverse event evaluation		X	X	X	X	X	X	X	
Radiologic evaluation	X								X ^e
Digital rectal exam and proctoscopic or sigmoidoscopic exam									X ^e
Pregnancy test ^f	X								

A: IPdR: Dose as assigned; PO QD administered throughout radiation (38 days, 6 weeks)
 B: Capecitabine: 825 mg/m² PO BID on days of radiation therapy (taken Monday morning through Friday evening each week of RT)
 C: Radiation therapy: 1.8 Gy/day × 28 doses (50.4 Gy total dose), M-F Days 1-5, 8-12, 15-19, 22-26, 29-33, 36-38
 a: Performance status evaluations are to be conducted every 4 weeks.
 b: Albumin, alkaline phosphatase, total bilirubin, bicarbonate, BUN, calcium, chloride, creatinine, glucose, LDH, magnesium, phosphorus, potassium, total protein, SGOT [AST], SGPT [ALT], sodium.
 c: 10 mL Blood for PK studies in sodium heparin tubes will be drawn on Day 8, prior to IPdR dose; and then after IPdR dose at 30 min, 60 min, 120 min and 240 min. On Day 21 and Day 35, blood will be drawn at 1-2 hours after the IPdR dose.
 d: 5 mL blood for measuring IUDR incorporation in granulocytes will be drawn in EDTA tubes prior to IPdR dose on Day 8, and at 1-2 hours after the IPdR dose on Day 21 and Day 35.

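### Section 3.1.13 sets a contraception period after the last dose for men (4 months after IPdR) but none for women, on one shared fetal-risk rationale and without explanation

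*Combined protocol and SAP*

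**What the plan says.** Section 3.1.13 says that the fetal effects of IPdR are unknown and requires contraception for that reason and "because radiosensitizing agents as well as other therapeutic agents used in this trial are known to be teratogenic". One sentence applies this to women of childbearing potential and to men, with the methods and period given as "hormonal or barrier method of birth control; abstinence) prior to study entry and for the duration of study participation". A later sentence, about men only, sets the period as "for the duration of study participation, and 4 months after completion of IPdR administration". There is no matching sentence for women.

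The same section defines a woman of childbearing potential as "any female who has experienced menarche and who has not undergone surgical sterilization (hysterectomy or bilateral oophorectomy) or who is not postmenopausal".

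Section 3.2.11 excludes pregnant women because "IPdR may have the potential for teratogenic or abortifacient effects". After a remark on breastfeeding it adds: "These potential risks may also apply to other agents used in this study".

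Study participation is not defined. The calendar in Section 11 has two columns that could mark its end: "Wk 10 (4 wks following chemoRT) End of study for toxicity assessment" and "Wk 14-18 (8-12 wks following chemoRT) End of study for response assessment". Section 6.8 gives 4 weeks of follow-up after treatment or removal from study, and Sections 6.6 and 6.8 place surgery 8 to 12 weeks after treatment.

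**The concern.** The hazard named in 3.1.13 is the same for both sexes, and 3.2.11 treats IPdR as a possible direct hazard to a pregnancy in a woman who takes it. Yet only men have a period that runs from the last dose. By adding 4 months for men, the plan implies that participation alone is too short for them. It does not say why participation alone is enough for a woman who took the same drugs herself.

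Followed as written, the rule lets a treated woman stop contraception weeks before a treated man. Because her rule follows participation rather than dosing, it can also lapse if she leaves the study early. What is at stake is avoidable fetal exposure or harm in a small number of women. The MTD, DLT, PK and response analyses do not depend on it.

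**Working it through.** The plan gives no figure of its own here, so the check compares the two rules and measures the distance between their end points.

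**Inputs**
- Men: 4 months after completing IPdR (3.1.13). Taken as 120 days; four calendar months run from 31+28+31+30 = 120 to 31+31+30+31 = 123 days.
- Women: until participation ends (3.1.13). Candidate end points are surgery at 8 to 12 weeks (6.6, 6.8 and the response column of the calendar) and the 4-week follow-up (6.8 and the toxicity column).
- Common start: Section 7.2.2 continues IPdR through the last radiation dose, so on the planned schedule IPdR is completed on the last treatment day.

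**Gap = men's period minus the day on which women's cover ends**

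| Women's cover ends at | Days after treatment | Gap at 120 days | Gap at 123 days |
|---|---|---|---|
| Surgery, 12 weeks | 12 × 7 = 84 | 120 − 84 = 36 | 123 − 84 = 39 |
| Surgery, 8 weeks | 8 × 7 = 56 | 120 − 56 = 64 | 123 − 56 = 67 |
| 4-week follow-up | 4 × 7 = 28 | 120 − 28 = 92 | 123 − 28 = 95 |

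**Which reading is more natural.** The calendar schedules an examination, laboratory tests, CEA and the resection itself at Weeks 14-18. Section 5.1 makes the surgical specimen mandatory, and 6.8 places response assessment at surgery. A woman who completes the study is therefore still participating at surgery, so 36 to 64 days is the main figure and 92 days the weaker one.

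**IPdR stopped early.** Section 7.3 lets radiation continue when IPdR is discontinued. If IPdR ends k days before the last treatment day, the men's period ends k days sooner and each gap falls by k. With surgery at 12 weeks the gap closes only at k = 36, which is Day 2 of the planned 38-day course (38 − 36 = 2).

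**Early withdrawal.** The men's 4 months run from the end of IPdR whether or not they stay in the study. If a woman's participation ends on the day she withdraws, her cover after dosing can be nil. If the 4 weeks after removal in 6.8 count as participation, it is 28 days.

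**Other text on pregnancy.** Section 10.5 requires reports of pregnancy in a patient or partner up to 90 days after the last dose. This is a reporting rule and sets no contraception period, but it treats the sexes alike. Women's cover ends before that window closes on every reading: 90 − 84 = 6 and 90 − 56 = 34 days (surgery), or 90 − 28 = 62 days (4-week follow-up). Section 6.5 lists pregnancy as a reason to stop treatment and tells women to report a suspected pregnancy; it sets no duration either.

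**The case against.** The strongest reply is that a difference between the sexes is not in itself an error. Risk through the mother and risk through sperm take different routes and can call for different periods. Section 2.2.1.1 gives the active metabolite, IUdR, a plasma half-life under 5 minutes after a bolus, against which even 28 days is long. This stands as a reason why the right periods might differ, but it does not settle the matter. The plan gives no such explanation, calls the fetal effects of IPdR unknown, and describes a drug that acts by incorporation into DNA, for which plasma half-life is not the only relevant measure. The text available for review gives no half-life for IPdR itself.

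A second reply is that few women are affected. Section 9.2 plans for at most 11 + 4 = 15 women among 30 patients of all ages. By then they will have had mFOLFOX6, 50.4 Gy to the pelvis and, on the natural reading, rectal surgery. This stands, and it limits the weight of the point. The definition of childbearing potential nevertheless exempts only surgical sterilization and menopause, so the rule still governs the women who remain.

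A third is that a period for women may be stated elsewhere. Consent pages were not available for review. Sections 8.1.3 and 8.2 point to the Investigator's Brochure and the capecitabine package insert, which were not available either. If one of them states a period, 3.1.13 should match it.

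A reader might infer that women have no cover at all after dosing. The documents do not support that: participation runs some weeks past the last dose for anyone who stays in the study. What is missing is a stated interval.

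**Conclusion.** The point holds as an unexplained difference with a practical consequence. On one shared rationale, men have a contraception period anchored to the last IPdR dose and women do not. For a woman who completes the study, cover most naturally ends at surgery, about 36 to 64 days before the men's period (39 to 67 if the four months are the longest in the calendar). This assumes that IPdR ends with radiation, as planned. The figure of 92 to 95 days rests on participation ending at the 4-week follow-up and should not be quoted as the main result. Early withdrawal could leave little or no cover.

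A reader might also infer that 4 months is the correct period for women. The documents do not establish that; they show only that the sponsor chose it for men. The number of women of childbearing potential is not stated and is probably small. The matter merits an amendment for patient safety and has no bearing on any analysis.

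**What to change.** Amend 3.1.13 so that women of childbearing potential use contraception through participation and for a stated period after the last dose. That period should be no shorter than the men's 4 months unless the sponsor's clinicians state and justify another length. Use one starting point for both sexes: completion of IPdR, or the last study drug dose if that is later. Using the later date for women only would create a new mismatch when IPdR stops before capecitabine. Align the consent text if it differs.

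The cost is a small edit to 3.1.13 and possibly to the consent text, with no added visits or procedures. The downside is a longer commitment for the few women affected, about 36 to 64 days beyond surgery at 4 months. Men whose IPdR stops before capecitabine would also have a slightly longer period.
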